10.2.2. Prohibited Concomitant Therapies

Administration of eculizumab is prohibited during the study. If the Investigator decides to administer eculizumab, the subject should be withdrawn from the study.

10.3. Treatment Compliance

Intravenous doses of the study drug are to be administered by study personnel. Administration dates and times must be recorded in the CRFs. If any portion of a dose of study drug is not administered, an explanation must be provided in the source document and on the CRF.

When subjects are receiving SC OMS721, treatment compliance will be determined by study drug reconciliation and patient interviews before dispensing drug supplies for the next visit interval.

10.3.1. Definition of Departure from Protocol

A protocol deviation is defined as any non-adherence to study procedures or schedules, as specified by the protocol.

10.4. Safety Monitoring

The Sponsor's Medical Monitor will monitor safety data in an ongoing manner throughout the study. An independent Data Monitoring Committee (DMC) will meet (in-person or telephonically) and review cumulative data every four months and after approximately 40 patients in the full analysis set (Section 13.2.4.2) have been followed for at least 26 weeks. The DMC will review all serious adverse events on an ongoing basis as they occur. Following each meeting (or as needed between meetings), the chairperson of the DMC will provide in writing one of the following recommendations to the Sponsor: 1) continue the study as planned, 2) continue the study under an amended protocol describing the recommended amendment, 3) suspend enrollment in the study pending provision of additional information, 4) suspend treatment in the study pending provision of additional information, or 5) discontinue the study. The DMC recommendation will also include the reasons upon which the recommendation is based. The DMC recommendations will be filed in the trial master file and included as an appendix in the clinical study report.

11. ASSESSMENT OF EFFICACY

This study evaluates efficacy, PK, PD, immunogenicity, and exploratory measures.

11.1. Primary Efficacy Measure

- Platelet count change from baseline

11.2. Secondary Efficacy Measures

The secondary efficacy measures include:

- Complete TMA response defined as normalization of platelet count, normalization of serum LDH, and > 25% decrease in serum creatinine on at least 2 consecutive measures over at least 4-weeks.

[figure not shown]
[figure not shown]
CONFIDENTIAL

No use, disclosure or reproduction outside of Omeros without prior written authorization

- Duration of complete TMA response measured from the time of the first measurement of complete TMA response to the last consecutive measurement of complete TMA response.
- Time to complete TMA response measured by the time to reach the first measurement of complete TMA response.
- TMA event-free status during treatment defined as no decrease in platelet count of $> 25\%$ from baseline, no plasma exchange or plasma infusion, and no initiation of new dialysis for at least 12 consecutive weeks.
- Time to TMA event-free status measured by the time to reach the first documented TMA event-free status from the first dose of OMS721
- Increase of $> 15 \text{ ml/min}/1.73 \text{ m}^2$ in eGFR calculated by the MDRD Equation for subjects aged ≥ 18 years and the Schwartz equation for subjects < 18 years.
- Time to eGFR increase of $> 15 \text{ ml/min}/1.73 \text{ m}^2$ measured by the time to reach the first measurement increase in eGFR of $> 15 \text{ ml/min}/1.73 \text{ m}^2$ from the first dose of OMS721
- Hematological normalization defined as normalization of platelet count and normalization of serum LDH on at least 2 consecutive measurements over at least 4 weeks.
- Time to hematological normalization measured by the time to reach the first measurement of hematological normalization from the first dose of OMS721
- TMA remission defined as platelet count $\geq 150,000/\mu\text{L}$ on at least 2 consecutive measures over at least 2 weeks.
- Quality of life as measured by EQ-5D-5L.
- Serum creatinine change from baseline.
- Serum LDH change from baseline.
- Serum haptoglobin change from baseline.
- Rate of TMA interventions defined as the number of dialysis events, plasma infusion events and plasma exchange events per subject per day.

11.3. Pharmacokinetic Measures

Serial serum samples will be collected according to the Schedule of Events (Section 19) for analysis of OMS721 concentration.

11.4. Pharmacodynamic Measures

Serial serum samples will be collected according to the Schedule of Events (Section 19) for analysis of the PD measure of inhibition of *ex vivo* lectin pathway activation.

CONFIDENTIAL

[figure not shown]
No use, disclosure or reproduction outside of Omeros without prior written authorization

11.5. Immunogenicity Measures

Serial serum samples will be collected according to the Schedule of Events (Section 19) for analysis of ADA.

11.6. Exploratory Measures

11.7. Quality of Life Assessments

Patient quality of life (QoL) will be assessed using the EQ-5D-5L instrument (EuroQol Research Foundation, Rotterdam, The Netherlands). This questionnaire-based tool is widely validated, available in multiple languages, and is used to quantify preference-based health states based on patient health ratings on the day that they are administered the questionnaire.

Questionnaires will be administered to each patient according to the Schedule of Events (Sections 19.1, 19.2, 19.3, and 19.4).

11.8. Health Economic Data Review

Health economic data related to treatment and outcomes of aHUS will be collected. These data will include dialysis treatment, plasma therapy treatment, and other aspects of health care utilization.

12. ASSESSMENT OF SAFETY

Investigators are responsible for monitoring the safety of subjects who have entered this study and for alerting the Sponsor to any event that seems unusual, even if this event may be considered an unanticipated benefit to the subject. The Investigator is responsible for appropriate medical care of subjects during the study.

Contact information for the Sponsor's Medical Monitor for this study is provided in Section 1.2.

12.1. Safety Parameters

Safety will be evaluated by assessing AEs, SAEs, clinical laboratory tests, vital signs, physical examination, and ECG. Only clinically significant (per Investigator opinion) changes in physical examination, vital signs, ECGs, or laboratory tests accompanied by clinical symptoms or those that require medical intervention will be reported as AEs.

CONFIDENTIAL

No use, disclosure or reproduction outside of Omeros without prior written authorization

12.1.1. Laboratory Tests

For evaluation of some of the laboratory assessments, a central laboratory will be used for all of the sites. The name and address of the clinical laboratory are included in the Investigator file.

The following laboratory assessments will be performed in this study:

- Chemistry tests include lactate dehydrogenase, haptoglobin, glucose, urea nitrogen, creatinine, total protein, albumin, total bilirubin, alkaline phosphatase, alanine aminotransferase, aspartate aminotransferase, calcium, sodium, potassium, chloride, and bicarbonate.
- Hematology tests include white blood cell count with automated differential (neutrophils, segmented neutrophils, lymphocytes, monocytes, eosinophils and basophils), schistocytes per HPF, red blood cell count, hemoglobin, hematocrit, mean corpuscular volume, mean corpuscular hemoglobin, mean corpuscular hemoglobin concentration, red cell distribution width, and platelet count.
- Coagulation tests include prothrombin time (PT), International Normalised Ratio (INR), and activated partial thromboplastin time (aPTT).
- Urinalysis tests include color, specific gravity, pH, glucose, protein, bilirubin, urobilinogen, blood, ketone, nitrite, leukocyte esterase and microscopic if required (red blood cells, white blood cells and bacteria).

12.1.2. Other Safety Measures

- Vital signs include systolic and diastolic BP, pulse rate, RR, and temperature.
- ECG parameters include heart rate, PR interval, QRS interval, QT interval, and QTc interval calculated by Fridericia's formula (QTcF), along with a clinical interpretation by the Investigator.

12.2. Definition of Adverse Events

12.2.1. Definition of Adverse Events

The following definitions from the International ICH Guideline E2A will apply to the reporting of AEs and adverse drug reactions:

Adverse Event: Any untoward medical occurrence in a patient or clinical investigation subject administered a pharmaceutical product and which does not necessarily have to have a causal relationship with this treatment.

Adverse Drug Reaction: All noxious and unintended responses to a medicinal product related to any dose.

The phrase, "responses to a medicinal product" means that a causal relationship between a medicinal product and an adverse event is at least a reasonable possibility, i.e., the relationship cannot be ruled out.

Unexpected Adverse Drug Reaction: An adverse reaction, the nature or severity of which is not consistent with the Investigator's Brochure.

CONFIDENTIAL

No use, disclosure or reproduction outside of Omeros without prior written authorization

Serious Adverse Event: Any untoward medical occurrence that at any dose:

- Results in death
- Is life-threatening
 - The term “life-threatening” refers to an event in which the subject was at risk of death at the time of the event; it does not refer to an event, which hypothetically might have caused death if it were more severe.
- Requires inpatient hospitalization or prolongs existing hospitalization
- Results in persistent or significant disability/incapacity
- Is a congenital anomaly/birth defect

Serious adverse events also include important medical events that may not be immediately life-threatening or result in death or hospitalization but may jeopardize the subject or may require intervention to prevent one of the other outcomes listed in the definition above. Examples of such events are intensive treatment in an emergency room or at home for allergic bronchospasm; blood dyscrasias or convulsions that do not result in hospitalization; or development of drug dependency or drug abuse.

12.2.2. Definitions of Severity

Adverse events will be graded using the Common Terminology Criteria for Adverse Events (CTCAE) v.4.0 [USDHHS 2009].

Note that “seriousness” and “severity” are distinct concepts. “Serious” is a term applied to an AE that meets specific requirements (refer to Section 12.2.1). “Severity” refers to the AE intensity classification.

12.2.3. Relationship to Study Drug

The Investigator will determine the assessment of the causal relationship of the AE to the study drug.

The relationship of AEs to study drug is categorized as probable, possible, unlikely, or not related. An alternative etiology must be provided for all AEs for which the relationship to study drug is considered “possible”, “unlikely”, or “not related.”

Definitions of each of these terms are below:

Probable: The AE has a timely relationship to administration of the study drug and there is no apparent, potential alternate etiology.

Possible: The AE has a timely relationship to administration of the study drug and there is an apparent, potential alternate etiology.

Unlikely: The adverse event is likely related to an etiology other than administration of study drug.

Not Related: The AE is related to an etiology other than the study drug.

CONFIDENTIAL

No use, disclosure or reproduction outside of Omeros without prior written authorization

An AE with causal relationship not initially determined will require follow-up to assign causality.

12.2.4. Assessment of the Clinical Outcome of Adverse Events

The Investigator (a study physician) will determine the clinical outcome of the AE as follows:

Recovered Completely: Subject has fully recovered from the event with no residual effects observable.

Recovered with Sequelae: Effects of the event are stabilized and constant. The likelihood of these effects changing (improving or worsening) is low.

Not Yet Recovered: Effects of the event are still present and changing. The event is not considered recovered completely or recovered with sequelae.

Unknown; Lost to Follow-up: Not known, not observed, not recorded, or refused to provide information.

Died: The event may or may not be the primary cause of death (may or may not be the immediate cause of death).

12.3. Reporting Adverse Events

12.3.1. Adverse Event Reporting

Adverse events will be collected from the time informed consent is obtained until the last Follow-Up visit. All AEs will be documented in the source records and will be recorded in the CRFs as appropriate. All AEs, whether observed by the Investigator or reported by the subject, and whether or not thought to be related to the study drug, will be recorded on the appropriate CRF. In describing AEs on the CRF, standard, medically accepted terminology will be used.

The description of each adverse event will identify the date of onset, duration, severity (see Section 12.2.2 for Definitions of Severity), any action taken (including any diagnostic procedures or laboratory tests performed and all treatments which were administered), the outcome of the event, and relationship to the study drug.

Any medical condition that is present at the time that the subject is screened should be considered as baseline and not recorded as an AE. However, if the medical condition increases in frequency or severity during or following administration of the study drug, it will be recorded as an AE on the appropriate CRF.

An AE is defined as any untoward medical occurrence in a subject administered a pharmaceutical product and which does not necessarily have to have a causal relationship with this treatment. Adverse events may be reported by the subject, discovered by the Investigator and Investigator's staff, or detected through physical examination, laboratory test, or other means.

Adverse events include:

- Any unfavorable and unintended sign, medical diagnosis, or symptom that occurs between the time of the first administration of study drug and the study duration required by the protocol.

CONFIDENTIAL

No use, disclosure or reproduction outside of Omeros without prior written authorization

- Any new undesirable medical experience or an unfavorable and unintended change of an existing condition that occurs between the time of the first administration of study drug and the study duration required by the protocol, whether or not considered related to study drug.
- Abnormal laboratory findings considered by the Investigator to be clinically significant, i.e., those that are unusual for the population being studied or individual subject.

Whenever possible, the Investigator should group signs or symptoms that constitute a single diagnosis into a single event term. For example, cough, rhinitis, and sneezing might be grouped together as *upper respiratory tract infection*.

In cases where the Investigator notices an unanticipated benefit to the subject, study site personnel should enter *unanticipated benefit* with the actual event term (for example, the complete actual term would be *unanticipated benefit-sleeping longer*).

12.3.2. Serious Adverse Event Reporting

All SAEs will be:

- recorded on the appropriate SAE case report form.
- followed through resolution or at a stable condition by a study physician.
- reviewed by a study physician.

The investigative site is required to report any SAE directly to the Sponsor's pharmacovigilance designee on the Serious Adverse Event form within 24 hours of becoming aware of the event, whether or not the SAE is deemed drug-related (see Section 1.2 for contact information).

The study physician will complete an Expedited or Serious Adverse Event Form within the following timelines:

- All deaths and immediately life-threatening events, whether related or unrelated to study drug, will be recorded on the Expedited or Serious Adverse Event Form and faxed/electronically communicated within 24 hours of site awareness.

Other supporting documentation of the event may be requested by the pharmacovigilance staff and should be provided as soon as possible.

A distinction is drawn between serious and severe events. A severe event is a major experience of its type. A severe event does not necessarily need to be serious. For example, nausea that persists for several hours may be considered severe nausea, but not a serious adverse experience. On the other hand, a stroke that results in only a limited degree of disability may be considered a mild stroke, but it would be considered a serious adverse event.

Death is an outcome of an event and not an event per se (sudden death or death of unexplainable causes can be reported, but follow-up will be required until cause of death is determined).

CONFIDENTIAL

No use, disclosure or reproduction outside of Omeros without prior written authorization

12.3.3. Reporting of Serious Adverse Events to Regulatory Agencies

The Sponsor or its designee will submit the SAEs requiring expedited reporting to regulatory agencies. The ethics committee will be notified of SAEs in accordance with federal, national, and local laws and regulations.

12.3.4. Pregnancy and Overdose Reporting

Cases of pregnancy must be reported for tracking purposes. If a subject becomes pregnant during the study, the Sponsor's Pharmacovigilance designee must be notified by fax or email within 24 hours of site awareness and the subject discontinued from study drug. Additional instructions for reporting of the pregnancy and outcome will be provided by the Sponsor at the time of notification. Pregnancies of partners of male subjects will also be followed provided the subject's partner provides informed consent for follow-up of the pregnancy.

Occurrences of overdose should be reported to the Sponsor for tracking purposes. Overdose is defined as any dosing above the protocol-defined dosing instructions. Additional instructions for reporting overdose information will be provided by the Sponsor at the time of notification.

12.4. Type and Duration of the Follow-Up of Subjects After Adverse Events

All reportable AEs will be followed until satisfactory resolution or until the Investigator deems the event to be chronic or the participant to be stable.

If an SAE persists at the last visit or the time of early termination after study treatment, it will be marked as "ongoing" and "not yet recovered" in the CRF. It will be followed by the Investigator until such time that it is deemed to be resolved or at a stable condition. Follow-up data for such SAEs will be collected in the source documents and reported appropriately.

12.5. Appropriateness of Measurements

12.5.1. Efficacy Measures

Measures of TMA activity include the following tests: platelet count, hemolysis (serum LDH, serum haptoglobin, hemoglobin, schistocytes), and organ dysfunction (e.g., serum). The need for continued plasma therapy or renal dialysis is medically relevant and also reflects aHUS activity. These measures are relevant for evaluation of aHUS activity and are individual endpoints or part of composite endpoints in this study. The EQ-5D-5L is a relevant and accepted measure of health-related quality of life.

12.5.2. Pharmacokinetic Measures

Drug concentrations are standard PK measures.

12.5.3. Pharmacodynamic Measures

Inhibition of *ex vivo* lectin pathway activation is a relevant PD measure as this is the biological target of OMS721.

CONFIDENTIAL

No use, disclosure or reproduction outside of Omeros without prior written authorization

12.5.4. Immunogenicity Measures

ADA response is a standard immunogenicity measure for a therapeutic protein. Samples demonstrating the presence of ADA will undergo testing to determine if the ADA titer and if the ADA are neutralizing.

12.5.5. Safety Measures

Adverse events, SAEs, clinical laboratory tests, vital signs, physical examination, and ECG are standard safety measures.

13. STATISTICS

13.1. Determination of Sample Size

The sample size is based on the plasma therapy-resistant cohort. Assuming that the true mean platelet count change from baseline is $78 \times 10^9 / \text{L}$ with a standard deviation of $64 \times 10^9 / \text{L}$ [Legendre 2013], a sample size of 56 plasma therapy-resistant subjects will provide 90% power to test a null mean platelet count change from baseline of $45 \times 10^9 / \text{L}$ at two-sided significance level of 5% using t-test. It is assumed that 70% of the eligible subjects will be plasma therapy-resistant. Therefore, the total sample size is 80 subjects who meet the full analysis set criteria.

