- Serum creatinine change from baseline
- Serum LDH change from baseline
- Serum haptoglobin change from baseline
- Rate of TMA interventions defined as the number of dialysis events, plasma infusion events and plasma exchange events per subject per day over the treatment period
- PK of OMS721
- PD of OMS721
- ADA

Statistical Methods:

Determination of Sample Size

The sample size is based on the plasma therapy-resistant cohort. Assuming that the true mean platelet count change from baseline is $78 \times 10^9/\text{L}$ with a standard deviation of $64 \times 10^9/\text{L}$ (Legendre, et al., 2013), a sample size of 56 plasma therapy-resistant subjects will provide 90% power to test a null mean platelet count change from baseline of $45 \times 10^9/\text{L}$ at two-sided significance level of 5% using t-test. It is assumed that 70% of the eligible subjects will be plasma therapy-resistant. Therefore, the total sample size is 80 subjects who meet the full analysis set criteria.

Analysis Populations

The full analysis set (FAS) will include all subjects who receive any amount of study treatment and have at least one post-baseline platelet count. The primary efficacy analyses will be based on the FAS.

The safety analysis set will include all subjects who receive any amount of study treatment. The safety analyses will be based on the safety analysis set.

Efficacy Analyses

The plasma therapy-resistant cohort will be the primary subject cohort for the evaluation of efficacy of OMS721. All efficacy analyses will be performed separately for the plasma therapy-resistant cohort and the plasma therapy-responsive cohort. Primary efficacy analyses will be based on the FAS. Supportive efficacy analyses will be based on the safety analysis set.

The primary efficacy endpoint (platelet count change from baseline) will be summarized descriptively by visit and cohort during the treatment period (induction and maintenance). A

CONFIDENTIAL

No use, disclosure or reproduction outside of Omeros without prior written authorization

repeated measures model with time and baseline platelet count as fixed effects, and subject as random effect will be used to evaluate the primary endpoint by cohort. A generalized estimating equation (GEE) method will be applied to estimate the least-squares mean change from baseline with 95% confidence interval at each scheduled time point.

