13.2.4. Multiple Comparisons and Multiplicity

This is a single-arm study with one primary efficacy endpoint. No multiplicity adjustment is necessary.

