13.2.14. Interim Analysis

One interim analysis is planned when approximately 40 patients in the FAS have been followed for at least 26 weeks. The purpose of the interim analysis is to provide an extensive safety and efficacy data review in addition to the regular safety monitoring. The study will not be stopped for efficacy based on the interim data and, therefore, no multiplicity adjustment is required.

The interim analysis will include, but not be limited to, the primary analyses of the efficacy and safety endpoints, and PK analysis. The DMC and the Sponsor will review the interim data and make recommendations according to the DMC charter.

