4. ANALYZED OBJECTIVES

4.1. Primary Objective

The primary objective of this study was to evaluate the effect of OMS721 in subjects with aHUS on platelet count change from baseline. As a sufficient number of patients were not enrolled, data for the primary objective will be not analyzed.

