9. EFFICACY ANALYSIS

9.1. General Considerations

This study was discontinued due to the inability to recruit a meaningful number of subjects; therefore, no efficacy analyses will be performed. Analyses that will be performed are outlined in this SAP.

Omeros Corporation

Statistical Analysis Plan (Abbreviated) - Protocol No. OMS721-HUS-002

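### The stated sample size and power do not match: on the protocol's own inputs, 56 plasma therapy-resistant subjects give about 97% power, not 90%; 90% needs 42

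*Protocol*

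**What the plan says.** Protocol section 13.1 (Determination of Sample Size) bases the sample size on the plasma therapy-resistant cohort. It assumes a true mean platelet count change of 78 × 10⁹/L and a standard deviation of 64 × 10⁹/L, both attributed to a published eculizumab study, with a two-sided 5% significance level and a t-test. It then states that "a sample size of 56 plasma therapy-resistant subjects will provide 90% power to test a null mean platelet count change from baseline of" 45 × 10⁹/L. The synopsis repeats the claim: "a sample size of 56 plasma therapy-resistant subjects will provide 90% power".

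The total of 80 follows from the assumption that 70% of eligible subjects will be resistant. Section 13.1 defines these 80 as subjects who meet the full analysis set criteria. It gives no dropout rate or other margin.

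Two passages bear on the significance level. Section 13.2.4 says of this single-arm study with one primary endpoint: "No multiplicity adjustment is necessary". Section 13.2.14 says: "The study will not be stopped for efficacy based on the interim data and, therefore, no multiplicity adjustment is required".

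**The concern.** The sentence in section 13.1 supplies every quantity that a one-sample power calculation needs, so the stated pair of 56 subjects and 90% power should be reproducible from it. It is not: 56 is well above what 90% power requires.

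This sentence is the only justification given for the targets of 56 resistant and 80 total subjects. A reader who checks it cannot tell whether the power is misstated, whether a different standard deviation, null or significance level was used, or whether an allowance was added and not written down. Anyone who reuses the calculation would carry forward a pair that does not fit its inputs.

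**Working it through.** **Inputs (Protocol section 13.1, repeated in the synopsis; means and SD in 10⁹/L)**

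- True mean change 78, null mean change 45, so the difference is 78 − 45 = 33.
- Standard deviation 64, so the standardised effect is 33/64 = 0.516.
- Two-sided α = 0.05, t-test. The study is single-arm (section 13.2.4), so this is a one-sample test.
- Stated result: n = 56, power 90%.

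**Attempt to reproduce the plan's figure**

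With df = n − 1, noncentrality λ = (33/64)·√n and critical value t = t(0.975, n − 1), exact power is P(T > t) + P(T < −t), where T is noncentral t with parameters df and λ.

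| n | λ | t | Power |
|---|---|---|---|
| 41 | 3.302 | 2.021 | 89.6% |
| 42 | 3.342 | 2.020 | 90.4% |
| 56 | 3.859 | 2.004 | **96.6%** |

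The stated pair does not reproduce. Power at 56 is 96.6 − 90 = 6.6 percentage points above the stated value, and 90% power needs 56 − 42 = 14 fewer subjects. A simulation of 400,000 trials at n = 56 gave 96.7%.

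**Can the gap be explained?**

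- *Rounding of the inputs.* Let the mean, the null and the SD each be off by 0.5.
  - Least favourable corner (difference 32, SD 64.5): power at 56 is 95.4%, and 45 subjects give 90%.
  - Most favourable corner (difference 34, SD 63.5): power at 56 is 97.6%, and 39 subjects give 90%.
- *Normal approximation.* n = ((1.960 + 1.282) × 64/33)² = 39.5, so 40 subjects. Power at 56 is Φ(3.859 − 1.960) = 97.1%. The gap widens.
- *One-sided 5%.* 34 subjects give 90%, and power at 56 is 98.5%. The gap widens.
- *Stricter α.* Two-sided 2.5% needs 50 subjects and two-sided 1% needs 60. To get 90% at 56, α would have to be about 0.0135. The text states 5%, and sections 13.2.4 and 13.2.14 rule out an adjustment.
- *Two-sample formula.* This gives 80 per arm and does not fit a single-arm study.
- *Another SD or null.* Changing one input at a time, 90% power at 56 requires an SD of about 74.8, or a difference of about 28.2, that is a null of 78 − 28.2 = 49.8. Neither is stated.
- *Attrition allowance.* 42/0.75 = 56, so a 25% loss would give exactly 56. No such rate is stated.

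**Step to the total**

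56/0.70 = 80 is correct. The same step from 42 would give 42/0.70 = 60.

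**The case against.** The best counter-argument is the attrition reading. An allowance of 25% turns 42 into exactly 56, and the design makes one plausible: the endpoint is the change to week 26 (section 7.3.1), the full analysis set requires only one post-baseline platelet count (section 13.2.4.2), and analyses use observed data without imputation (section 13.2.4.1). A subject could therefore be in the full analysis set with no week-26 value. On that reading both numbers could be right and the defect would be an omission. The replacement figure of 97% would then overstate power for a week-26 t-test if a quarter of the values were missing. In addition, the planned primary analysis is a repeated-measures model adjusted for baseline (section 13.2.8.1), so 97% describes only the planning calculation.

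Part of this stands. The 97% does assume that all 56 subjects contribute a value, and the source of 56 cannot be recovered from the documents. But the allowance is written nowhere. Section 13.1 attaches the 90% directly to 56 subjects, names a t-test as the basis, and defines the 80 as subjects who already meet the full analysis set criteria. If an allowance was used, its omission is what needs correcting.

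It is also fair to say that 56 subjects do deliver at least 90% power, so the sentence would hold as a floor. The text does not say "at least", and a floor would still leave the choice of 56 rather than 42 unexplained.

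**Conclusion.** The stated pair is wrong as written. On the protocol's inputs, 56 plasma therapy-resistant subjects give 96.6% power, and 42 are enough for 90%. Over the full rounding range of the inputs, power at 56 is 95.4% to 97.6% and the number needed for 90% is 39 to 45. These figures rest on a one-sample two-sided t-test with every counted subject contributing a value. The documents do not show which half of the pair is wrong, or whether an unstated input or allowance lies behind it.

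Severity is minor. The error is conservative, so the study is not underpowered on its inputs. It also has no remaining effect on results: the study was discontinued, SAP section 4.1 says "data for the primary objective will be not analyzed", and SAP section 9.1 says "no efficacy analyses will be performed". This is a correction of the record.

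**What to change.** The sponsor should first check how 56 was obtained.

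- If it includes an allowance for missing values, or if a different standard deviation, null or significance level was used, state that input so that the pair reproduces.
- If there is no such input, restate the sentence in section 13.1 and the synopsis to say that 56 plasma therapy-resistant subjects provide about 97% power and that 42 would provide 90%.

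Keep the targets of 56 resistant and 80 total subjects. The cost is one sentence in two places, with no change to patient numbers, visits or analyses.
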